2.6 Study outcome evaluations

2.6.1 Study endpoints

Primary endpoints

- The co-primary endpoint is feasibility, which will be defined as successful by 90% of enrolled participants completing the 2-week study visit.
- The co-primary endpoint is an intention-to-treat assessment of the difference in mean PrepDM Scale in the intervention versus control arms of the study at the 2-week study visit.

Secondary endpoints

- Difference in mean confidence-weighted true false (CTF) knowledge score will be measured in the intervention versus control arms of the study. CTF scoring adds points for certainty in correct responses and deducts points for certainty in incorrect responses. Participants receive +2 points when "sure" about a correct response, +1 if unsure about a correct response, -1 if unsure about an incorrect response and -2 if sure about an incorrect response. For a 14-item knowledge test, the maximum score is +28 and the minimum score is -28, with higher scores indicating more knowledge about lung transplant.
- Decisional Conflict Scale change will be measured from the baseline study visit to the 2-week study visit. The intention-to-treat analysis will compare mean change in the Decisional Conflict Scale between the intervention and control arms of the study. Scores range from 0 [no decisional conflict] to 100 [extremely high decisional conflict].
- Likert rating of preparedness will be measured at the 2-week study visit (0=Don't know, 1= Not at all prepared, 2 = A little prepared, 3 = Moderately prepared, 4 = Very prepared). The intention-to-treat analysis will compare mean Likert-scale rating between the intervention and control arms of the study.
- PHQ-9 is a scale that measures symptoms of depression in the prior 2 weeks on a 0-27 scale, with higher scores indicating worsening depression and a score of 10 or higher consistent with a diagnosis of depression. Investigators will assess the difference in mean PHQ-9 score in the intervention versus control arms of the

study at the 2-week study visit. Investigators will also determine the proportion with new PHQ-9 score greater than or equal to 10 in each arm.

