- GAD-7 is a scale that measures symptoms of anxiety in the prior 2 weeks on a 0-21 scale, with higher scores indicating worsening anxiety and a score of 10 or higher consistent with a diagnosis of generalized anxiety disorder. Investigators will assess the difference in mean GAD-7 score in the intervention versus control arms of the study at the 2-week study visit. Investigators will also determine the proportion with new GAD-7 score greater than or equal to 10 in each arm.
- Longitudinally characterize time spent using Take on Transplant through analysis of patient-level usage data. Average time spent using the research website from baseline to 2 weeks will be compared across study arms. Further, time spent using the investigator-designed website will be assessed as a predictor of: 1. change in CTF knowledge about LTx (14-question investigator-designed survey) from baseline to 2-week study visit, 2. change in Likert preparedness from baseline to 2-week study visit, 3. change in Decisional Conflict Scale from baseline to 2-week study visit, and 4. mean PrepDM Scale at 2-weeks.
- The PrepDM Scale will be measured for all participants with respect to Take on Transplant and mean score will be compared for participants in the intervention (4 weeks of exposure) versus control arms (2 weeks of exposure). PrepDM scores range on a scale from 0 to 100 with higher scores indicating a higher perceived level of preparation for decision making.
- Identify baseline demographic and health literacy predictors of increased tool usage.

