2.6.3 Statistical analysis plan

Primary endpoints

The co-primary endpoint is feasibility, which will be defined successful by 90% of enrolled participants completing the 2-week study visit (V2). Descriptive statistics will be used to determine whether this threshold was met.

The co-primary endpoint of difference in PrepDM scale score (Difference = intervention – control) at 2-weeks will be assessed using linear regression, with statistical significance level set at 2-sided alpha <0.05.

Secondary endpoints

Continuous secondary endpoints will be assessed using linear regression, with statistical significance level set at 2-sided alpha <0.05.

Categorical secondary endpoints will be assessed using Pearson's chi-squared test of independence, with statistical significance level set at 2-sided alpha <0.05.

Graphical methods and descriptive statistics will be used to evaluate differences in usage during the 4 weeks of access across subsets of the cohort with different socioeconomic

status (based on insurance status, income, education level) and health literacy (based on S-TOFHLA). Exploratory models will test for a dose-response relationship by 1) time spent using the tool (uses/week) and 2) number of ‘CF Stories’ viewed and PrepDM Scale at 2-week and 4-week study visits. Linear regression may be used to determine whether predictors of increased time spent using the tool can be identified from baseline demographics and questionnaire results. Subgroup analyses will compare changes across instruments among participants with adequate health literacy to those with inadequate or marginal health literacy. We will also perform subgroup analysis for patients with $FEV_1 < 30\%$ predicted.

These data will inform the feasibility of completing a larger, multicenter, randomized controlled trial of ToT and will inform duration of the larger trial.

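### The secondary comparisons of arm means name no covariates, so baseline (V1) scores and the FEV1 stratum are left out (except V1 by subtraction in Decisional Conflict); this costs precision, not validity

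*Combined protocol and SAP*

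**What the plan says.** Section 2.6.3 covers all continuous secondary endpoints in one sentence: "Continuous secondary endpoints will be assessed using linear regression, with statistical significance level set at 2-sided alpha <0.05". The co-primary PrepDM difference has the same form: "at 2-weeks will be assessed using linear regression, with statistical significance level set at 2-sided alpha <0.05". Neither sentence names a covariate, and neither says the model is unadjusted.

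Section 2.6.1 (repeated in the synopsis) defines the arm contrasts:

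- CTF knowledge: "Difference in mean confidence-weighted true false (CTF) knowledge score will be measured in the intervention versus control arms of the study". No visit is named.
- Likert preparedness, measured at 2 weeks: "The intention-to-treat analysis will compare mean Likert-scale rating between the intervention and control arms of the study".
- PHQ-9: "Investigators will assess the difference in mean PHQ-9 score in the intervention versus control arms of the" study; the sentence goes on to name the 2-week visit.
- GAD-7: "Investigators will assess the difference in mean GAD-7 score in the intervention versus control arms of the study at the 2-week study visit".
- Decisional Conflict: "The intention-to-treat analysis will compare mean change in the Decisional Conflict Scale between the intervention and control arms of the study".

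Baseline values are available. Section 2.5.8 schedules PHQ-9 and GAD-7 at V1. The Decisional Conflict endpoint starts from baseline. The website-time analysis in 2.6.1 uses change from baseline in CTF and Likert. For PHQ-9 and GAD-7, V1 is also needed to count new scores of 10 or more in each arm.

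Section 2.5.3 stratifies randomisation by FEV1 below 30% versus 30–50%. In the analysis, FEV1 below 30% returns only as a subgroup.

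**The concern.** A score measured before exposure usually predicts the same score two weeks later, and including it in the regression removes that part of the residual variance. The plan will hold these scores and uses some of them in the website-time models, yet leaves them out of the randomised comparison of means for four of the five instruments. For Decisional Conflict, subtracting V1 fixes its coefficient at 1 instead of estimating it.

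With about 22 and 23 completers per arm, chance baseline differences are not rare, and an unadjusted difference in 2-week means carries them through in proportion to the V1–V2 correlation. The stake is wider intervals on estimates meant to inform a larger trial. PHQ-9 and GAD-7 are also the named safety assessments. Separately, silence on covariates leaves their choice open until the data have been seen.

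**Working it through.** **The plan's own figure.** Section 2.6.2 gives 90% of 50 with a 95% CI of 79–96%. The Wilson interval for 45/50 has centre (0.9 + 3.8415/100)/(1 + 3.8415/50) = 0.871 and half-width (1.96/1.0768) × √(0.09/50 + 3.8415/10,000) = 0.085. That gives 78.6–95.7%, so the figure reproduces. The documents give no SD, correlation, effect size or power for any secondary endpoint.

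**Inputs.** From the documents: 1:1 allocation and 45 completers, taken as 22 and 23. Assumed: the V1–V2 correlation r, and the ratio k = SD(V2)/SD(V1).

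**Chance imbalance.** The SE of a baseline difference is √(1/22 + 1/23) = 0.298 SD. P(|difference| > 0.5 SD) = 2 × (1 − Φ(0.5/0.298)) = 2 × (1 − Φ(1.677)) = 0.094, about 9% for a given scale.

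**Adjusted analysis against 2-week means (CTF, Likert, PHQ-9, GAD-7).** The variance ratio is (1 − r²) × penalty. The penalty for estimating coefficients is 1 + 1/41 = 1.0244 for V1 alone and 42/40 = 1.05 if the stratum is charged in full. Equivalent completers are 45/ratio. Detectable differences use the noncentral t with 41 df (43 df unadjusted, giving 0.85 SD).

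| r (assumed) | Variance ratio | Change in variance | Equivalent completers | Detectable at 80% power |
|---|---|---|---|---|
| 0.1 | 1.014–1.040 | +1 to +4% | 43–44 | – |
| 0.3 | 0.932–0.956 | −4 to −7% | 47–48 | 0.83–0.84 SD |
| 0.5 | 0.768–0.788 | −21 to −23% | 57–59 | 0.75–0.76 SD |
| 0.7 | 0.522–0.536 | −46 to −48% | 84–86 | 0.62–0.63 SD |

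Break-even is r = √(1 − 1/penalty) = 0.15 to 0.22. Simulated trials (8,000 per setting, stratified blocks, both covariates fitted) agree: cuts of 6.0–7.0%, 22.1–23.4% and 46.1–48.4% at r = 0.3, 0.5 and 0.7, and a loss of 1–2% at r = 0.1.

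**Adjusted analysis against raw change (Decisional Conflict).** The ratio is k²(1 − r²) × penalty/(1 + k² − 2rk).

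| k (assumed) | Cut at r = 0.3 | Cut at r = 0.5 | Cut at r = 0.7 |
|---|---|---|---|
| 0.8 | 47–49% | 40–42% | 34–36% |
| 1 | 32–33% | 21–23% | 11–13% |
| 1.25 | 18–20% | 6–9% | −3 to 0% |

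**Validity.** With no true effect, random dropout and an assumed 0.5 SD difference between strata (6,000 simulated trials per setting), bias was zero to two decimals for all three analyses. Rejection rates were 4.6–4.8% (2-week means), 4.6–4.9% (change) and 4.5–5.1% (V1-adjusted). In a deliberately extreme case, where dropout depended on V1 in opposite directions by arm (about 10% missing, r = 0.6), 2-week means were biased by −0.13 SD and change by +0.09 SD, each rejecting about 6% of the time. The V1-adjusted estimate was nearly unbiased.

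**The stratum.** Adding it to a V1-adjusted model left the SE at 0.263 at r = 0.5. For PrepDM, which has no described V1 value, the SE without and with the stratum was 0.297 and 0.297 if strata do not differ. It was 0.305 and 0.298 if they differ by 0.5 SD, and 0.328 and 0.298 at 1.0 SD. These gaps, and 30% of participants in the low stratum, are assumptions.

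**The case against.** The strongest reply is that an unadjusted comparison of randomised arms is legitimate, that these are secondary endpoints of a pilot, and that section 2.6.2 makes no power claim for them. That stands, and it limits the priority.

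It is also fair that the size of the loss is not a trial figure. Across the assumed values, adjustment runs from 4% more variance to 48% less against 2-week means, and from 3% more to 49% less against raw change. Nothing in the documents places this trial within those ranges.

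Four stronger readings are tempting, and the documents do not support them:

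- **That the SAP has decided against adjustment.** It is silent. The loss figures apply if the endpoint definitions are taken at face value.
- **That the V1 data go to waste.** They enter the Decisional Conflict change, the new PHQ-9 and GAD-7 cases by arm, the website-time models and the health-literacy subgroup comparisons of change.
- **That V1 scores are contaminated by website exposure.** Section 2.5.2 introduces the website during V1 and lets baseline-day interviews ask about it. But Appendix 1 places the intro session before randomisation and aims to learn participants' understanding before they see any website. That largely answers the point.
- **That the stratum omission is material for PrepDM.** A visible loss needs a large stratum effect, for which the documents give no basis.

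**Conclusion.** The point holds as a matter of efficiency. The V1 score is left out of four comparisons of means and enters the fifth only by subtraction; the stratum enters none. The gain from adjustment is small at a correlation of 0.3, worthwhile at 0.5 and large at 0.7, with a slight loss below about 0.2. For Decisional Conflict it also depends on the SD ratio and can vanish. Nearly all of the gain comes from the V1 score.

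A reader might infer that the planned estimates are biased or the tests invalid. They are not, provided dropout does not depend on V1 score differently by arm. That proviso matters because about 45 of 50 participants would be analysed. Omitting a stratum that does predict the outcome makes the test conservative (3.5–3.8% rejection with an assumed 1 SD gap), not too liberal. Priority is low to moderate.

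**What to change.** In section 2.6.3, for CTF (at 2 weeks), Decisional Conflict, Likert preparedness, PHQ-9 and GAD-7, state the model as: 2-week value = arm + V1 value of the same instrument + FEV1 stratum (<30% vs 30–50%). Report the adjusted arm difference with its 95% CI. The Decisional Conflict change endpoint can stay, because change regressed on the same covariates gives the identical arm difference. Keep raw means and mean changes as descriptive summaries, and the new-case proportions as planned.

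Add the stratum to the PrepDM model because it is a randomisation factor, with little gain expected. Add one line that V1 scores are recorded before website access, as Appendix 1 suggests is intended.

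The Likert coding ("0=Don't know, 1= Not at all prepared") places non-answers below the lowest rating and needs its own rule. That is a separate issue. It should not be solved by excluding those participants, since a 2-week answer is given after randomisation and exclusion would break the intention-to-treat comparison.

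The cost is SAP wording and no new data. Each secondary model gives up two degrees of freedom and PrepDM one, with a slight loss of precision if the correlation is below about 0.2.

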2.4.2 Anticipated number of research subjects

The study will enroll approximately 50 adults with CF and an FEV₁<50% predicted, without prior LTx. Individuals will be recruited from the University of Washington and collaborating adult CF centers across the United States.

We anticipate 90% (45 participants) of enrolled participants will complete the 2-week study visit.

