2.5.3 Allocation to treatment arms

Participants will be randomized 1:1 to either the intervention (“Take on Transplant”) or the attention control (unos.org), stratified by $FEV_1 < 30\%$ versus 30-50%. Participants will be given access to their assigned website via the research website portal for two weeks. After the 2-week session interview, access to the opposite arm assignment will be unlocked and participants will have unlimited access to both the intervention (ToT) and the attention control (Unos.org).

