2.6.2 Sample size determination

This will be a pilot and feasibility study, and we anticipate 90% of 50 enrolled participants (95% CI 79-96%) will complete the 2-week study visit (V2).

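### The secondary endpoints carry an unadjusted 0.05 significance rule with no exploratory label, and a chi-squared test is a weak summary of the two psychological-harm proportions

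*Combined protocol and SAP*

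**What the plan says.** Section 2.6.3 gives two general rules for secondary endpoints. For continuous ones: "Continuous secondary endpoints will be assessed using linear regression, with statistical significance level set at 2-sided alpha <0.05". For categorical ones: "Categorical secondary endpoints will be assessed using Pearson's chi-squared test of independence, with statistical significance level set at 2-sided alpha <0.05". The co-primary PrepDM comparison in the same section has the same two-sided 0.05 level.

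No section ranks the secondary endpoints, adjusts for their number, or says that their p-values are descriptive. The word exploratory is attached only to the dose-response models for PrepDM. Three other groups are treated more loosely in 2.6.3: usage by socioeconomic status and health literacy is graphical and descriptive, regression for usage predictors is optional, and the subgroup analyses have no stated alpha.

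Section 2.6.1 lists the secondary endpoints, beginning with knowledge: "Difference in mean confidence-weighted true false (CTF) knowledge score will be measured in the intervention versus control arms of the study". For new PHQ-9 or GAD-7 scores of 10 or more, it says only that the proportion in each arm will be determined.

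On size and purpose, section 2.6.2 states: "This will be a pilot and feasibility study". Section 2.4.2 adds: "We anticipate 90% (45 participants) of enrolled participants will complete the 2-week study visit".

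**The concern.** When many endpoints each have their own 0.05 rule and nothing says how they rank, any one that crosses the line can be reported as a significant finding. The 5% level then describes each test alone and not the set. A pilot meant to shape a larger trial could carry forward an outcome that stood out by chance.

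The two harm proportions raise the opposite problem. Section 2.5.8 says that transplant education might worsen depression, anxiety or suicidality and uses PHQ-9 and GAD-7 to look for this. As categorical secondary endpoints, the proportions with a new score of 10 or more fall under the chi-squared rule. With so few participants and probably few events, that test will usually be non-significant whether or not harm has increased.

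**Working it through.** **The plan's own figure.** Section 2.6.2 gives a 95% CI of 79-96% for 90% completion among 50. The Wilson interval for 45/50 is 78.6-95.7%, which rounds to the stated range. Wald (81.7-98.3%), Clopper-Pearson (78.2-96.7%) and Agresti-Coull (78.2-96.1%) do not. This is the only calculated figure in the sample-size section; the documents state no error rate for the secondary endpoints as a set.

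**Count of tests, from 2.6.1.**
- Nine between-arm comparisons: CTF knowledge; Decisional Conflict change; Likert preparedness; mean PHQ-9; new PHQ-9 of 10 or more; mean GAD-7; new GAD-7 of 10 or more; website time to week 2; and PrepDM for Take on Transplant at 4 versus 2 weeks of exposure.
- Four models with website time as predictor: of CTF change, Likert change, Decisional Conflict change and 2-week PrepDM.
- Total 13. Usage predictors and subgroups are left out because the plan fixes no number for them.

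**Chance of at least one p<0.05 with no true effects.** For k independent tests it is 1 − 0.95^k:
- k = 9: 1 − 0.95^9 = 0.370
- k = 13: 1 − 0.95^13 = 0.487

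For correlated tests I took two-sided normal test statistics with a common pairwise correlation and integrated numerically. The correlations are assumptions.

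| Tests counted | corr. 0 | 0.3 | 0.5 | 0.7 |
|---|---|---|---|---|
| 9 arm comparisons | 37% | 33% | 27% | 20% |
| 12 (without time vs 2-week PrepDM) | 46% | 40% | 32% | 23% |
| All 13 | 49% | 42% | 33% | 24% |

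At correlation 0.8 the 13-test figure is 19%.

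As a cross-check, I used a simulation with 23 and 22 completers, a 10% rate for the two proportions, usage time independent of outcome, and the time models fitted in the intervention arm only. As the correlation among outcomes rose from 0 to 0.7, the chance fell from 35% to 26% for the nine comparisons and from 47% to 36% for all 13. Because usage time is independent there, not all tests are correlated and the fall is smaller.

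**The two harm proportions.** About 45 completers allocated 1:1 gives 22 and 23 per arm. The documents give no event rates, so those below are illustrative. Exact power of Pearson's test at 0.05, with the two values showing which arm has 23:
- 5% versus 15%: 19.7% or 17.1%
- 10% versus 20%: 16.7% or 14.3%

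With rare events the test is also conservative: its true size is 1.6% when both rates are 5%, and 4.4% when both are 10%.

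**What an interval would show.** Suppose 2/22 versus 2/23, again illustrative. The difference is 0.0909 − 0.0870 = 0.004. The Wilson limits are 0.025 to 0.278 and 0.024 to 0.268. Newcombe's limits are:
- lower: 0.004 − √[(0.0909 − 0.0253)² + (0.2680 − 0.0870)²] = −0.189
- upper: 0.004 + √[(0.2781 − 0.0909)² + (0.0870 − 0.0242)²] = 0.201

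Equal event counts therefore leave an excess of about 20 percentage points unexcluded, which a p-value does not show.

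**The case against.** The best defence is that this is a pilot, its primary and secondary endpoints are separated, and unadjusted secondary endpoints are common in such studies. That stands, and it is why the point has modest weight and calls for labelling rather than a multiplicity procedure.

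Several stronger readings are tempting, and the documents do not support them.
- **That every secondary analysis carries a significance claim.** It does not: see the looser wording for dose-response, predictors, subsets and subgroups. Time against 2-week PrepDM is listed as secondary in 2.6.1 but falls within the models that 2.6.3 calls exploratory. The two harm proportions reach a test only through the general chi-squared sentence. Without those two, seven arm comparisons remain, at 1 − 0.95^7 = 30% if independent and 18% at correlation 0.7.
- **That 24-49% is the chance of a false claim that the tool works.** It counts results in either direction and includes tests of usage. Eight of the arm comparisons concern outcomes other than website time. Counting only results favouring the tool, the chance is 1 − 0.975^8 = 18% if independent, and lower with correlation.
- **That the small sample drives the error rate.** The rate depends on the number of tests and their correlation, and hardly at all on having 45 completers. Sample size matters for precision and for sparse tables.
- **That the plan will read a non-significant result as no harm.** No section says so. Safety monitoring rests on review of individual PHQ-9 responses, physician follow-up and adverse event probing, and 2.6.4 rules out statistical monitoring for safety termination. The objection to the chi-squared test is that it carries little information about harm.

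**Conclusion.** The concern holds in a limited form. Section 2.6.3 sets significance levels for the secondary endpoints and does not say how a significant result is to be interpreted. With no true effects, at least one p<0.05 in either direction would occur about 20-37% of the time over the nine arm comparisons and 24-49% over all 13. These figures rest on my count of tests from 2.6.1 and on assumed correlations of 0.7 down to 0. A stricter count or stronger correlation lowers them; adding predictor or subgroup tests raises them.

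For new PHQ-9 or GAD-7 scores of 10 or more, power of about 14-20% for a 10-point rise, under assumed rates, means that a non-significant chi-squared result would be uninformative about safety. The PrepDM co-primary analysis is untouched. This is a cheap improvement to a pilot plan and not a flaw in its main result.

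**What to change.** In section 2.6.3:

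1. State that secondary, predictor and subgroup results are exploratory and will be reported as estimates with 95% CIs. Any p-values are to be described as unadjusted and not a basis for efficacy claims.
2. For the proportions with new PHQ-9 and new GAD-7 scores of 10 or more, replace the chi-squared test with the between-arm risk difference and its Newcombe 95% CI, and state the largest excess in the intervention arm that the interval does not exclude.

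The cost is a few sentences, with no change to visits, data or sample size. The downside is that secondary results can no longer support confirmatory significance claims. The estimates and intervals are also what planning the larger trial would need.

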Research website – Participants will be introduced to the research website during the baseline session (V1). The research website is a portal that will contain links to two interventions including ToT and an attention control (unos.org). Before accessing the research website during the baseline session, participants will be randomized to first receive access to only one of the two websites through the portal. The research website will track website usage (i.e. time spent, content accessed, etc.) for all study participants for both ToT and unos.org. Once the participant completes the 2-week study visit (V2), the portal will contain access to both ToT and unos.org for the remainder of the study (2 more weeks).

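### The usage analyses assume 4 weeks of access to Take on Transplant for the whole cohort, but controls have 2; subset and predictor comparisons should use a common window or include arm

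*Combined protocol and SAP*

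**What the plan says.** Section 2.6.3 plans graphs and descriptive statistics for "differences in usage during the 4 weeks of access across subsets of the cohort", the subsets being defined by socioeconomic status and health literacy. It adds that linear regression may be used to see "whether predictors of increased time spent using the tool can be identified from baseline demographics and questionnaire results". Neither sentence mentions arm, length of access, or a window that is the same for everyone.

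The design gives unequal access to Take on Transplant. Under section 2.5.2, "participants will be randomized to first receive access to only one of the two websites through the portal"; after the 2-week visit, "the portal will contain access to both ToT and unos.org for the remainder of the study (2 more weeks"). Section 2.6.1 states the consequence outright for the final PrepDM comparison: "participants in the intervention (4 weeks of exposure) versus control arms (2 weeks of exposure").

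Two parts of the plan do take account of access time. The between-arm comparison of time on the research website (section 2.6.1) is limited to baseline to 2 weeks, when each arm has one site. The exploratory dose-response models (section 2.6.3) express time spent as uses per week, without saying which weeks form the denominator.

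**The concern.** Specific Aim 2 asks who uses Take on Transplant more, and the synopsis rationale wants to know whether people from disadvantaged backgrounds use it differently. Total time on the tool depends on the person and on how long the tool was open to them. Here the second factor differs two-fold by arm.

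Randomisation is stratified only by FEV₁ (below 30% versus 30-50%, section 2.5.3). Nothing forces the literacy, insurance, income or education subsets to be balanced across arms. If a subset happens to hold more intervention participants, it will tend to show more use even when weekly behaviour is identical; the reverse imbalance could hide a real difference. The results are meant to inform the larger trial and its duration, so an access artefact read as engagement could mislead that planning.

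**Working it through.** **Is there a figure in the plan to reproduce?** Not for usage: no mean, SD, effect size or power is given. The one computed figure in section 2.6.2, 79-96% around 90% of 50, is reproduced by the Wilson interval for 45/50 (78.6-95.7%), but it has no bearing on this point.

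**Inputs from the documents.** Access to Take on Transplant: 4 weeks (intervention) versus 2 (control). Allocation 1:1. About 50 enrolled, 45 expected at the 2-week visit. Communities of concern at least 30%, so 0.30 × 50 = 15. Sizes of the individual literacy and education subsets are not given; 15 is used as an illustration.

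**Step 1: access.** The ratio is 4/2 = 2.0. At 1:1 the pooled mean is (4 + 2)/2 = 3 weeks.

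**Step 2: expected bias.** Arm is assigned independently of baseline traits, so the expected difference between subset and remainder in the share with 4 weeks of access is zero.

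**Step 3: chance imbalance.** The number of intervention participants in the subset is hypergeometric. For 15 of 50 with 25 per arm, the difference in shares has

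SD = √[0.25 × (50/49) × (1/15 + 1/35)] = 0.156.

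| Difference in shares at least | 15 of 50 | 15 of 45 (22 v 23 per arm) |
|---|---|---|
| 10 points | 54% | 53% |
| 20 points | 22% | 21% |
| 30 points | 6% | 6% |

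**Step 4: what an imbalance does.** Take 10/15 of the subset and 15/35 of the remainder in the intervention arm. Mean access is 2 + 2 × 10/15 = 3.33 weeks versus 2 + 2 × 15/35 = 2.86 weeks. If use is proportional to access, the apparent difference is 3.33/2.86 − 1 = 17% with identical weekly behaviour. An imbalance this large in either direction has probability 22%. In general, 20 points shifts mean access by 2 × 0.20 = 0.4 weeks, or 0.4/3 = 13% of the pooled mean.

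**Step 5: added variance (assumptions, shown as a range).** Let mean total minutes be μ₄ and μ₂ in the two arms, with log-normal spread s between people and c² = exp(s²) − 1, which is 0.284 for s = 0.5 and 1.718 for s = 1.0.

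- Between-arm variance B = ((μ₄ − μ₂)/2)²
- Within-arm variance W = c²(μ₄² + μ₂²)/2
- Variance ratio, no arm term to arm term: (W + B)/W, divided by 44/43 = 1.023 for the chance correlation of arm with subset when n = 45

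The assumed means are 60 v 30 min (use proportional to access) and 60 v 48 min (front-loaded use, totals differing 1.25-fold).

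| μ₄ v μ₂, s | B | W | Ratio | Simulated SD of contrast: no arm / arm / per week |
|---|---|---|---|---|
| 60 v 30, 0.5 | 225 | 639 | 1.352/1.023 = 1.32 | 9.4 / 8.2 / 7.6 |
| 60 v 30, 1.0 | 225 | 3866 | 1.058/1.023 = 1.03 | 20.4 / 19.9 / 18.6 |
| 60 v 48, 0.5 | 36 | 838 | 1.043/1.023 = 1.02 | 9.3 / 9.3 / 10.9 |
| 60 v 48, 1.0 | 36 | 5072 | 1.007/1.023 = 0.98 | 22.5 / 22.6 / 24.8 |

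The last column comes from 8,000 simulated cohorts of 45 with a subset of 15. It agrees with the formula to within simulation error; for example, (20.4/19.9)² = 1.05 against 1.03.

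**Step 6: minutes per week of access.** Rescale to the pooled 3 weeks. If use is proportional to access, both arms become 45 min, B vanishes, and the gain over no adjustment is (639 + 225)/(0.284 × 2025) = 1.50 at s = 0.5. If use is front-loaded, the arms become 60/4 × 3 = 45 and 48/2 × 3 = 72, so B = 182. At s = 0.5 the variance is 1024 + 182 = 1206 against 838 + 36 = 874, a rise of 38%. At s = 1.0 it is 6193 + 182 = 6375 against 5072 + 36 = 5108, a rise of 25%. The simulated SDs give 37% and 21%.

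**The case against.** **No systematic bias.** A reader might infer that the plan will misstate how disadvantaged participants use the tool in a predictable direction. The documents do not support that. Access is randomised, and chance imbalance is part of the sampling error of the unadjusted estimate. This stands in full.

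**The loss of precision may be trivial.** A reader might also infer that every predictor estimate becomes appreciably noisier. Only use proportional to access with a narrow spread gives a ratio near 1.3. Wider spread or early use brings it to about 1.0. This stands too.

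**The text is soft.** The subset comparison is descriptive, the regression is optional, and its covariates are not listed, so an arm term is not ruled out. That is fair, and it lowers the severity. But the window is stated, and for Take on Transplant it is wrong for half the cohort; following it as written gives a comparison with two-fold unequal access.

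**Usage might mean the portal**, which everyone has for 4 weeks. The objective in section 1.3.2, the synopsis rationale and the regression's reference to the tool all point to Take on Transplant. Even on the portal reading, the content available differs by arm in the first 2 weeks.

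**Uses per week already handles it.** That measure appears only in the dose-response models, with an undefined denominator. The other exposure there, the number of CF Stories viewed, is not a rate.

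**Conclusion.** The point holds as a minor one. The 4-week window in section 2.6.3 conflicts with the 4 versus 2 weeks of Take on Transplant access set by the design and stated in section 2.6.1, and no adjustment is specified for the subset and predictor analyses.

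Expected bias is zero. The harm is a chance of about 21-22% that a subset of 15 among 45 to 50 differs from the remainder by 20 points or more in arm mix, plus a variance ratio running from about 1.3 down to about 1.0. The first figure rests only on the assumed subset size. The second rests on usage means and spreads that the documents do not give. The FEV₁ subgroup is better protected, because FEV₁ is the stratification factor. Feasibility and the 2-week PrepDM comparison do not use these analyses and are unaffected.

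**What to change.** In section 2.6.3:

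1. Replace the single 4-week period with the actual Take on Transplant access in each arm.
2. For subset and predictor comparisons, use the first 2 weeks of Take on Transplant access in each arm (from the baseline session for intervention, from the unlock after the 2-week session for controls); or keep total use and include arm in the regression.
3. Show the descriptive plots by arm or by weeks since first access. This helps even with the common window, which equalises length but not context: controls reach the tool after 2 weeks of unos.org and with both sites open.
4. Keep per-week rates as a supplement, with the denominator defined as weeks of Take on Transplant access. They assume that use accrues evenly; if it is front-loaded they raise variance by roughly 20-40% and make the 4-week arm look less engaged.

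The cost is a few sentences. Arm is known and the portal already tracks use of both sites, so no new data are needed. The common window leaves weeks 3-4 of the intervention arm out of that comparison, though they can still be described separately. The arm term uses one degree of freedom.
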